9.2 Secondary study parameter(s)

All hypothesis testing will be explorative in nature, and thus secondary to describing the outcome measures. The confidence interval of the difference between groups will be used to test non-inferiority of conventional RF compared to cooled RF. In case the point estimate of the difference in proportion of treatment effect between groups will be below the non-inferiority limit, this will be suggestive of non-inferiority. In that case, we will use the results of this study to calculate the necessary sample size for a future randomized controlled non-inferiority trial.

Other secondary study parameters (MQS III, PGIC, duration of pain relief, OKS, the Timed Up and Go test, goniometry, HADS, PCS, EQ-5D-5L, performance of a TKA and the amount of Adverse Events and/or Serious Adverse Events) will be reported as mean or percentage difference including 95% confidence interval. Hypothesis testing will be performed using the independent t-test for continuous variables, and Fisher's Exact test for categorical variables. This will only be regarded as explorative in nature.

Cocogen Trial

COST EFFECTIVENESS ANALYSIS (CEA)

Economic evaluation comparing conventional to cooled RF treatment will be performed with a time horizon of 6 months. Cost-effectiveness will be assessed by evaluating the incremental cost-effectiveness ratios using several perspectives: societal cost per QALY (based on EQ-5D-5L), healthcare cost per reduced point on the pain score, and healthcare costs per additional treatment success. Standard bootstrap and sensitivity analysis will be performed to address uncertainty surrounding the findings.

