7.1.1 Main study parameter/endpoint

The primary study parameter is the proportion of patients with a pain reduction of at least 50% at three months post intervention. Pain intensity is expressed as a number from the numerical rating scale. Absolute NRS scores are also collected at each visit. A pain dairy of multiple NRS during 4 days will be collected to achieve a more complete and trustworthy idea of pain.

In this study we will use a threshold of 50% although IMMPACT guidelines only recommend a threshold of 30% because in the clinical setting the 50% threshold is most often used, as well in previous studies. This makes comparison within the literature easier.

NRS is a unidimensional, subjective measurement of pain intensity, expressed by the patient as a number between 0 and 10. It is a 11 point scale in which 0 equals no pain and 10 maximal pain. (35)

Furthermore, at one, three, six and twelve months post intervention the patients are also asked whether the pain is acceptable.

A month is defined as 30 days with 4 days before or after this timepoint.

At 12 months a time window of 2 weeks before and there the timepoint is accepted.

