7.1.2 Secondary study parameters/endpoints

The secondary parameters are:

 Patient self-reported impression of change, measured by the Patient's Global Impression of Change (PGIC) at 1, 3, 6 and 12 months. The impression of change is measured using a 7 point likert scale. (36)

Cocogen Trial

- The change in medication use, measured by the change in Medication Quantification Scale III (MQS III). The MQS is designed as a methodology of quantifying different drug regimens in 1992 and updated in 1998 (MQS II) and 2003 (MQS III) using detriment weights determined by surveying physician members of the American Pain Society. (37) This will be recorded at baseline, 1, 3, 6 and 12 months post intervention.
- The duration of pain relief. This is defined as the time interval in which a NRS reduction of more than 50% is obtained or in which the pain is still acceptable without the usage of other additional therapies (increase in MQS 3 score of more than 50%, intra-articular infiltration, operation)
- The change in physical function from baseline to 3, 6 and 12 months post intervention. This will be measured by the change in the Oxford Knee Score (OKS). (38) The OKS is a patient-reported measure assessing pain intensity and physical function. The list consists of 12 items scored from 1 to 5, with 0 representing normal function/ least symptoms. Objectively, knee function will be measured through goniometry by using the CJOrtho app and by 'timed up and go' test. (39, 40) The measurement of maximal knee flexion and extension is performed in a standardised manner and photos of each position will be kept for review. The 'Timed Up and Go' test assesses patients' functional mobility of the lower extremities. Participants are timed with a stopwatch while standing up from a chair, walking 3 meters (in a comfortable and safe way), come back and sit back in the chair. The objective parameters of physical function will not be obtained at 12 months.

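### Duration of pain relief is a censored time outcome, but the protocol summarises it as a mean difference with a t-test and no stated horizon; separately, its 50% threshold differs from the primary endpoint's

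*Protocol*

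**What the plan says.** Protocol section 7.1.2 makes duration of pain relief a secondary outcome, "defined as the time interval in which a NRS reduction of more than 50% is obtained or in which the pain is still acceptable", provided no additional therapy is used. The therapies that end it are given as "increase in MQS 3 score of more than 50%, intra-articular infiltration, operation".

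Section 9.2 names duration in the list that starts "Other secondary study parameters (MQS III, PGIC, duration of pain relief, OKS". The outcomes in that list "will be reported as mean or percentage difference including 95% confidence interval". The next sentence reads "Hypothesis testing will be performed using the independent t-test for continuous variables", with Fisher's exact test for categorical ones, and the section calls all of this exploratory. It names no time-to-event method for any outcome.

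On follow-up, section 3 gives 12 months with assessments at 1, 3, 6 and 12 months, and Appendix E lists a 12-month contact (T4) completed at home. Section 7.3 says follow-up lasts 6 months and lists contacts only up to T3.

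On the threshold, section 7.1.1 defines primary success through the "proportion of patients with a pain reduction of at least 50% at three months post intervention", whereas the duration definition asks for more than 50%.

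**The concern.** A patient still in relief at the last contact has no completed duration, only a lower bound. For a patient whose NRS response or acceptability has lapsed, the loss is known only to fall between two visits, and the last gap is six months wide. A mean and a t-test need one number per patient. They therefore treat the lower bound as the duration and fix the loss by some convention.

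This matters for two reasons. Section 7.2 names longer duration of success as a potential benefit of cooled RF. Section 4.4 says the pilot exists to estimate effect sizes of the primary and secondary outcomes for a later trial. A mean duration with no named horizon is hard to carry into that design.

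The two 50% thresholds are a separate matter of consistency: one patient's NRS response can be judged differently by two endpoints, and no reason is given.

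**Working it through.** **The plan's own figure.** The protocol states no effect size, SD or power for duration. Its only related number is the sample size in section 4.4: 12 patients × 2 arms × 2 populations = 48, which reproduces. That is 24 per arm overall and 12 per arm in each population.

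**1. Dependence on the horizon.** Assumption: exponential durations with mean m, because the protocol gives no duration data. If everyone is followed to a common time τ and censored times are entered as observed, the arm mean is m × (1 − exp(−τ/m)).

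Example, means 6 (conventional) and 12 (cooled) months:
- τ = 12: 6 × (1 − e^−2) = 5.19 and 12 × (1 − e^−1) = 7.59; difference 2.40.
- τ = 6: 6 × (1 − e^−1) = 3.79 and 12 × (1 − e^−0.5) = 4.72; difference 0.93.

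| Assumed means (months) | Difference, τ = 12 | Difference, τ = 6 | Ratio | In relief at 12 months |
|---|---|---|---|---|
| 3 v 6 | 2.24 | 1.20 | 1.9 | 2% v 14% |
| 6 v 9 | 1.44 | 0.59 | 2.4 | 14% v 26% |
| 6 v 12 | 2.40 | 0.93 | 2.6 | 14% v 37% |
| 12 v 24 | 1.86 | 0.59 | 3.2 | 37% v 61% |

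The same patients thus give a mean difference about 1.9 to 3.2 times larger under the 12-month statement than under the 6-month one.

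**2. Withdrawal while in relief.** A patient last seen in relief at 3 months and entered as 3 could have contributed up to 12, so the entry is up to 12 − 3 = 9 months short. One such patient lowers an arm mean by up to 9/12 = 0.75 months in an arm of 12, or 9/24 = 0.375 months in an arm of 24. The effect on the difference depends on how many such patients each arm has, which cannot be known in advance.

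**3. Visit spacing.** In 2,000 simulated trials per scenario with complete follow-up, each duration was entered as the last visit still in relief. With 24 per arm, the mean difference was 1.49 for means 6 v 9 (1.44 on exact times to 12 months), 2.55 for 6 v 12 (2.40) and 2.18 for 12 v 24 (1.86). The distortion is modest and in these cases upward.

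**4. The test.** In the same simulation with means 6 v 12, power for t-test and log-rank was 0.28 and 0.28 at 12 per arm, and 0.53 and 0.53 at 24 per arm. With equal means of 6, rejection rates were 0.047 and 0.050 at 12 per arm, and 0.059 and 0.060 at 24.

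**5. The thresholds.** Inclusion requires NRS above 4, so integer baselines run from 5 to 10. The highest follow-up score that meets each rule is:

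| Baseline | At least 50% | More than 50% |
|---|---|---|
| 5 | 2 | 2 |
| 6 | 3 | 2 |
| 7 | 3 | 3 |
| 8 | 4 | 3 |
| 9 | 4 | 4 |
| 10 | 5 | 4 |

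The rules part only at 6, 8 and 10, and in the same way in both arms.

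**The case against.** **Understatement.** A reader might infer that the planned mean understates a longer effect of cooled RF by a calculable share. For means 6 v 12, 2.40 against an unrestricted difference of 6.0 looks like a 60% loss. That compares two estimands. The figure of 2.40 is exactly the restricted mean difference to 12 months, which a sound time-to-event analysis would also report. The figure of 6.0 needs extrapolation beyond follow-up. With complete follow-up the t-test also holds its level and matches the log-rank test. This objection stands, and no percentage of bias is claimed.

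**Thresholds.** A reader might also infer that the wording adds to such a bias, or that an exact halving is always a primary success but never relief. Neither follows. The wording applies equally to both arms, and a patient with acceptable pain is in relief by the second route in section 7.1.2. That route is a deliberate composite and is not an error.

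**Dating of events.** Sections 4.2, 5.2 and 5.3 require other treatments to be documented, and the 12-month contact asks when any knee arthroplasty took place in the osteoarthritis group. Some events that end relief can therefore be dated between visits. Interval censoring concerns mainly the NRS and acceptability parts.

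**What the protocol leaves open.** The t-test reaches duration by implication, as a continuous variable. A censoring rule may stand in an SAP that is not at hand, and section 9 provides multiple imputation for incomplete records. The absence of such a rule is not the point; the summary and test that section 9.2 does state are. Imputation also does not complete the duration of a patient with full data who is still in relief at 12 months. Section 7.3 may be meant to describe site visits only, but it states the length of follow-up as 6 months.

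**Weight.** This is one exploratory secondary outcome in a pilot, and the sample-size step in section 9.2 uses the difference in proportions. That limits the consequences.

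**Conclusion.** The point holds in limited form. Section 9.2 gives a time outcome with right and interval censoring a summary and a test that ignore both. The resulting mean has no stated horizon, while the protocol gives two follow-up lengths. Under assumed exponential durations, that alone moves the difference by a factor of about 1.9 to 3.2. Withdrawal in relief can lower an arm mean by up to 0.75 months per patient in an arm of 12, for a patient last seen at 3 months. Visit spacing adds a smaller distortion.

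The documents do not support a fixed understatement of cooled RF, nor a loss of power or error control when follow-up is complete. The threshold mismatch is a real but separate inconsistency, confined to even integer baselines and without direction between arms. The change is worth making because estimation is the pilot's stated purpose, although the outcome is exploratory.

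**What to change.** 1. Take duration of pain relief out of the t-test list in section 9.2. Analyse it as time to loss of relief or additional therapy, right-censored at last contact. Use Kaplan-Meier or interval-censored curves by arm and a restricted mean difference to a named horizon with 95% confidence interval, stratified by osteoarthritis and post-arthroplasty group.
2. Reconcile the 12-month follow-up in section 3 and Appendix E with the 6 months in section 7.3, since this sets the longest horizon available.
3. Separately, reconcile the thresholds in sections 7.1.1 and 7.1.2, or state why they differ.

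The cost is a few lines of text and slightly more analysis work, with no new data collection. With 48 patients the curves and the restricted mean difference will have wide intervals, and the report should say so.

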3. STUDY DESIGN

This study is designed as a prospective, multicentre, double blind, randomised controlled non-inferiority pilot trial. The total follow up time is 12 months with follow up assessments at 1, 3, 6 and 12 months post intervention. It is estimated that the total duration of data collection will cover 2 year. Patients will be randomly selected for treatment with conventional RF treatment or cooled RF treatment of the SL, SM and IL genicular nerves. In total, three hospitals participate in this study: Ziekenhuis Oost-Limburg (Belgium), Maastricht UMC+ (Netherlands) and Rijnstate (Netherlands).

An overview of the main procedures that participants undergo is provided in figure 1, Appendix A.

Cocogen Trial

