- The change in health-related quality of life, measured by the change in EQ-5D-5L, between baseline and 6 and 12 months post intervention. (41) The EQ-5D-5L is a patient-reported generic measure of HRQoL comprising five dimensions: mobility, self-care, usual activities, pain/discomfort and anxiety/depression. Responses to the 5 items (one for each dimension) result in a patient's health state that can be transformed into a utility score ranging between 0 (death) and 1 (full health), representing the quality of life of the health state. (41). The EQ-5D-5L is assessed at baseline and at 1, 3, 6 and 12 months post intervention.
- Change in characteristic attitudes and symptoms of depression from baseline to 3, 6 and 12 months post intervention. This will be measured by the change in Hospital Anxiety and Depression Scale (HADS) and in Pain Catastrophizing Scale (PCS) from baseline to 6 and 12 months. (42, 43) HADS is developed to detect anxiety and depression in patients with physical health problems. The questionnaire consists of 14 items: 7 items to measure anxiety and 7 items to measure depression. The PCS is often used in clinical settings to measure catastrophic thinking related to pain. The 13 item questionnaire consists of 3 subscales (magnification, rumination and helplessness) and asks patients to

Cocogen Trial

reflect on past painful experiences and to indicate the degree on which they experiences each of 13 thoughts of feelings on a 5- point scale (0 not at all and 4 all the time).

- Amount of Adverse Events and/or Serious Adverse Events. Active capture during each site visit to assess specific symptoms and adverse events that are relevant to chronic knee pain or RF treatment.

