- Costs in both intervention groups. Costs include health care related costs (e.g. intervention cost, medication), costs to patients and family (e.g. travel costs, out-of-pocket payments), and costs due to lost productivity. Complete individual level hospital resource use data (e.g. surgical intervention, diagnostic procedures, hospital admissions, outpatient clinic visits) will be measured using medical records and by means of a self-developed questionnaire to be completed by patients, based on the iMTA Medical Consumption Questionnaire as recommended in the Dutch guideline for economic evaluation. (44) The questionnaire will have a recall period of 3 months and will be administered repeatedly at baseline, 3, 6 and 12 months post intervention. The Dutch manual for costing research will be used to determine prices for each volume of resource use. (45)
- Cost-effectiveness will be expressed using incremental cost-effectiveness ratios (e.g. incremental cost per QALY, incremental cost per reduced point on the pain score, and incremental costs per additional treatment success). QALYs (Quality Adjusted Life Years) will be calculated by multiplying life years with the health-related quality of life during these life years as measured by the EQ-5D-5L.
- At 12 months in the osteoarthritis group, we ask if a total knee arthroplasty is performed and if so at which timepoint.
- All used questionnaires to retrieve the above mentioned outcome parameters can be found in Appendix D.

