7.3 Study procedures

Patients will be in follow up for 6 months. There are 4 site visits. T0 to collect baseline parameters after which the intervention is performed. T1 at one month post intervention. T2 at 3 months post intervention at which the primary endpoint is collected. T3 at 6 months post intervention.

Table 1 (Appendix E) provides an overview of all study procedures per follow up moment. There is a distinction between study procedures at site and study procedures at home.

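### The economic evaluation stops at 6 months although costs, EQ-5D-5L and knee-replacement timing are collected to 12, and the month-12 cost form leaves patient-reported costs for months 6 to 9 without a stated source

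*Protocol*

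**What the plan says.** The cost-effectiveness paragraph of Protocol section 9.2 fixes the horizon: "Economic evaluation comparing conventional to cooled RF treatment will be performed with a time horizon of 6 months". It plans three ratios: societal cost per QALY, healthcare cost per point of pain reduction, and healthcare cost per additional treatment success.

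The rest of the protocol mostly works to 12 months:

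- Section 3: "The total follow up time is 12 months with follow up assessments at 1, 3, 6 and 12 months post intervention".
- Section 7.1.2, utilities: "The EQ-5D-5L is assessed at baseline and at 1, 3, 6 and 12 months post intervention".
- Section 7.1.2, cost form: "The questionnaire will have a recall period of 3 months and will be administered repeatedly at baseline, 3, 6 and 12 months post intervention".
- Section 7.1.2, surgery: "At 12 months in the osteoarthritis group, we ask if a total knee arthroplasty is performed and if so at which timepoint".
- Appendix E, Table 1 lists the cost diary, EQ-5D-5L and knee-replacement status at T4 (12 months).
- Section 4.2 allows other therapies, surgery included, during follow-up provided they are documented, and gives correct costing in the cost-effectiveness analysis as the reason.

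Section 7.3 differs: "Patients will be in follow up for 6 months. There are 4 site visits". The count of four site visits fits the Summary, which has four site visits plus one online visit. The 6-month duration does not fit the Summary or section 3.

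On cost sources, section 7.1.2 says hospital resource use "will be measured using medical records and by means of a self-developed questionnaire to be completed by patients". The cost categories also include "costs to patients and family (e.g. travel costs, out-of-pocket payments), and costs due to lost productivity".

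**The concern.** The economic question in the introduction (section 1) is whether the higher product cost of cooled RF is repaid by a higher success rate and perhaps a more durable effect. Section 7.2 repeats the possibility of longer-lasting success. The product cost falls on the day of treatment. Any return from durability, whether as better utility, less repeat care or later knee replacement, may come after month 6. A 6-month horizon cannot show that part, even though the patients are still being observed.

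The second issue is separate. If the sponsor later wants a 12-month analysis, the cost form as scheduled does not supply one complete set of costs. An analysis plan written afterwards can change a horizon, but it cannot recover costs that nobody asked about. The multiple imputation in section 9 is of little help, because the gap occurs in every patient by design and no patient has observed values for it.

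**Working it through.** The 6-month horizon is a design choice with no formula behind it, so there is no stated figure to reproduce. The check is one of coverage.

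**Inputs.** Horizon 6 months (section 9.2). Follow-up 12 months (section 3). Cost form at 0, 3, 6 and 12 months with 3-month recall (section 7.1.2). EQ-5D-5L at 0, 1, 3, 6 and 12 months (section 7.1.2). Cost diary also at month 1 (Appendix E).

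**1. Cost-form coverage.** A form at month t with recall r covers months t − r to t.

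| Form | Months covered after treatment |
|---|---|
| Month 3 | 0 to 3 |
| Month 6 | 3 to 6 |
| Month 12 | 9 to 12 |

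- 6-month horizon: 3 + 3 = 6 of 6 months covered, so there is no gap.
- 12-month horizon: 3 + 3 + 3 = 9 of 12 months covered. Months 6 to 9 are missing, and 3/12 = 25%.
- Adding the month-1 diary leaves both results unchanged.
- Adding a form at month 9, or giving the month-12 form a 6-month recall (covering 6 to 12), brings coverage to 12 of 12.

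**2. QALY time.** Assume QALYs are the area under the utility curve by the trapezoidal rule. The protocol does not name the rule. Each interval of length L months gives L/24 years of weight to each of its two ends.

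| Month | Weight, 6-month horizon | Weight, 12-month horizon |
|---|---|---|
| 0 | 1/24 = 0.042 | 0.042 |
| 1 | (1+2)/24 = 0.125 | 0.125 |
| 3 | (2+3)/24 = 0.208 | 0.208 |
| 6 | 3/24 = 0.125 | (3+6)/24 = 0.375 |
| 12 | not used | 6/24 = 0.250 |
| Sum (years) | 0.5 | 1.0 |

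The 6-month horizon uses half of the observed QALY time. With d6 and d12 as the between-arm utility differences at months 6 and 12, the omitted QALY difference is 0.25 × (d6 + d12). It is zero if both differences are zero, and it favours cooled RF only if their sum does.

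**3. What still covers months 6 to 9.** Medical records supply surgery, diagnostics, admissions and outpatient visits. The knee-replacement date is asked at month 12 in osteoarthritis patients. Sections 4.2, 5.2 and 5.3 require other therapies and medication to be documented, and a medication list is taken at T4. Travel, out-of-pocket payments, lost productivity and care outside the hospital record have no stated source for these months. They bear mainly on the societal cost per QALY; the other two ratios use healthcare costs.

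**4. Month-1 diary.** Appendix E has it and section 7.1.2 does not. Its look-back is not stated. If it were also 3 months, it would cover months −2 to 1 and overlap the month-3 form on months 0 to 1.

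**The case against.** The strongest defence is that 6 months is a legitimate choice. Section 7.2 unblinds patients at the 6-month follow-up, so later utilities and self-reported costs come from people who know their treatment. The economic analysis is a secondary goal of a 48-patient pilot. Section 2 describes it as an initial estimate for scoping the evaluation in the definitive trial. EQ-5D-5L at 12 months and knee replacement are still reported as secondary outcomes, so the later information is not lost. All of this stands, and it limits the weight of the point. But the protocol does not give unblinding, or anything else, as its reason for the horizon, and the horizon matches only the follow-up length in section 7.3 that section 3 contradicts.

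A reader might also infer four stronger things that the protocol does not support:

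- **That months 6 to 9 go uncosted.** Medical records and the knee-replacement date cover hospital care. The gap is in patient-reported costs.
- **That the recall gap keeps later data out of the planned analysis.** Only the horizon does that. Within 6 months the form's coverage is complete.
- **That the analysis favours conventional RF by construction.** That needs a real late advantage of cooled RF. The protocol calls this only a potential benefit, hypothesises non-inferiority, and expects similar effects in both groups.
- **That months 0 to 1 are counted twice.** Section 7.1.2 attaches the 3-month recall to months 0, 3, 6 and 12, and the form in Appendix D is not shown. Only the mismatch between the two schedules is documented.

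**Conclusion.** The point holds in a limited form and is worth acting on. The horizon omits half of the observed 12 months: 0.5 of 1.0 year of QALY time and every cost after month 6, including any knee replacement done then. No reason is given, and the follow-up statements in sections 3 and 7.3 disagree. If cooled RF lasts longer, the ratios carry its full initial cost and only part of its benefit. The size of that effect cannot be computed from the protocol, and it is nil if the arms do not differ after month 6.

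Separately, patient-reported costs for 3 of 12 months (25%) have no stated source. This is harmless at 6 months, but it prevents a complete 12-month societal cost. A 12-month QALY and hospital-cost analysis could already be done with the planned data. The conclusion assumes that the 3-month recall applies to the month-12 form as section 7.1.2 says. The weight is modest because the analysis is exploratory.

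**What to change.** 1. Reconcile sections 3, 7.3 and 9.2 on length of follow-up and economic horizon.
2. Add a 12-month cost-effectiveness analysis beside the 6-month one. State which is the base case and why, and note that data after month 6 come from unblinded patients.
3. Give the T4 cost form a 6-month recall, or add one online cost form at month 9. Either brings coverage to 12 of 12 months.
4. Make section 7.1.2 and Appendix E agree on the month-1 cost diary. If it stays, state the period it covers and that of the month-3 form, so that months 0 to 1 enter once.
5. Adjusting QALYs for baseline EQ-5D-5L utility is a sensible addition that needs no new data. Reporting net monetary benefit beside the ratios is optional.

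The cost is an amendment to the text and a reworded form. The 6-month recall is somewhat less reliable than a 3-month one; the alternative is one extra online form per patient. The change to the form has to be in place before patients reach the affected time points, because the missing costs cannot be recovered at analysis.
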